4 STUDY ENDPOINTS

4.1 Primary Endpoint

Progression free survival defined as the time from randomisation to the first of one of the following events or death from any cause:

- Clinically symptomatic progression requiring palliative tumour-specific oncological intervention (e.g. change in systemic therapy or localised non-SBRT radiotherapy) as determined by the treating physician.
 - New or existing intra-cranial lesions not amenable to radical surgery or SRS.
- Development of new extra-cranial lesions or progression of existing extra-cranial lesions not meeting the criteria for SBRT treatment (e.g. size >7cm)
- Development of >5 new or progressing extra-cranial lesion at any one point in time (i.e. widespread progression)

Progression will be assessed radiologically at each clinic visit following randomisation or more frequently if clinically indicated. The scans at time of trial entry will be used as the baseline for assessment. Determining progression of new or existing extra-cranial OP lesions, as stated above, will

be by assessment of % change of individual lesions compared to the baseline scan, with progression defined as a \geq 20% change from baseline in an individual lesion. In these instances, the criteria for determining progression meeting the primary endpoint definition will be based on an assessment of SBRT suitability as defined below. This method will be used to determine OPD in both the control and SBRT treatment groups to minimise bias in determining PFS events. The HALT virtual MDT should review progression events in both groups and research teams at participating centres will be required to upload the scans indicating further progressive disease for review.

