Central confirmation of suitability may be provided following review of tumour imaging and/or planning scans by the virtual MDT if requested by the local research team. A period >3 months since the last SBRT treatment is required before commencing repeat SBRT. However, repeat SBRT can be considered within a shorter time interval if an early interval scan has been requested by the vMDT, or where the total number of OPD lesions to be treated remain \leq 5 and this has been agreed by the vMDT.

Re-irradiation – Further SBRT treatment of progressing OPD lesions previously treated with SBRT either as part of the trial or prior to trial entry is not permitted in the HALT trial. Assessment of progression in previously treated OPD lesions should be as defined in Section 4 Primary Endpoint.

Disease Progression - Upon confirmation of disease progression meeting the primary endpoint no further post-treatment follow up assessments are required. Patients should continue to attend routine clinic visits as per local practice and the procedure upon further disease progression detailed below should be followed.

If disease progression is suspected in the period between 3 monthly visits (>1 month prior to next scheduled visit) (i.e. development of clinical symptoms suggestive of disease progression) all post-treatment follow-up assessments as detailed above should be conducted. If progression is confirmed and no further SBRT is possible (control group/lesion not suitable to SBRT) patients should follow the procedure upon further disease progression (Section 10.4) from their next scheduled visit.

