13 STATISTICAL CONSIDERATIONS

13.1 Statistical Design and Sample Size Justification

HALT is a randomised, multi-centre, phase II/III study with planned international participation. The integrated phase II/III trial incorporates a transition to full phase III dependent on feasibility data obtained during the phase II trial. This design offers the most efficient use of time and resource compared to a standalone phase II trial followed by a separate phase III trial and allows maximum return of information in a relatively short timeframe. Progression to the phase III trial will be dependent on emerging feasibility data from the phase II trial including recruitment rates; safety and extent of opportunities for international participation (see section 11.5). With the development of novel actionable mutations and TKIs continuing to emerge both the phase II and III components of the study have proposed adaptive aspects to allow inclusion of additional patient groups with OPD on any other targeted treatments as they are introduced into routine practice.

Limited data is available on oligo-progression in patients with NSCLC, however a median time from radiological oligo-progression to widespread progression when continuing on a TKI alone (as per the control group) of approximately 3 months was estimated following a survey of U.K. oncologists and clinical members of the trial team. Furthermore, most oncologists surveyed considered 3 months to be a suitable level of additional benefit for the addition of SBRT (experimental treatment) to be considered a worthwhile intervention. Therefore median PFS for the SBRT group is assumed to be 6 months. Using these estimates together with a significance level of 5% (two-sided), 90% power, a 2:1 allocation ration (SBRT treatment:control), 110 randomised patients (anticipated 73:37) in total is required to obtain 97 PFS events. The sample size calculation uses the log rank test due to the possibility of non-proportional hazards.

The sample size calculation assumes a recruitment period of 36 months with a 6 monthly accrual percentage of total of 5%: 10%: 15%: 20%: 25%: 25% with a minimum of 6 months follow-up (total duration 42 months). It is assumed that the lost to follow up rate will be <1% due to the frequency of follow-ups in line with routine practice and the short expected median time to reaching the primary endpoint.

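### The between-visit rule in Protocol Section 10.3 can take control patients off scheduled imaging before they have a PFS event, in conflict with its own preceding paragraph, Section 4.1 and Appendix A2

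*Protocol*

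**What the plan says.** **What counts as an event.** Under Protocol Section 4.1, extra-cranial progression is a PFS event when a lesion does not meet the SBRT criteria or when more than 5 lesions are new or progressing at one time. Symptomatic progression that needs palliative tumour-specific intervention, intracranial disease not amenable to radical surgery or SRS, and death also count. Of the suitability test, Section 4.1 says: "This method will be used to determine OPD in both the control and SBRT treatment groups to minimise bias in determining PFS events". Appendix A2 applies its flow chart at each extracranial scan and judges the intention to give SBRT, so that controls can be classified too. Section 11.6 treats progression that receives a further round of SBRT as short of the primary endpoint.

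**When assessment stops.** The disease-progression paragraph of Section 10.3 reads: "Upon confirmation of disease progression meeting the primary endpoint no further post-treatment follow up assessments are required". The next paragraph covers progression suspected more than 1 month before the next scheduled visit: "If progression is confirmed and no further SBRT is possible (control group/lesion not suitable to SBRT) patients should follow the procedure" in Section 10.4, starting at the next scheduled visit. Section 10.3 also restricts repeat SBRT to patients allocated SBRT.

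**What Section 10.4 collects.** It asks for patient status, current treatment, limited toxicity assessment and blood for ctDNA. Neither it nor the post-progression column of the Section 10.7 schedule lists tumour imaging.

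**The concern.** The two paragraphs of Section 10.3 use different tests. The first asks whether the primary endpoint has been met. The second asks whether more SBRT can actually be given, and for a control the answer is always no. Section 4.1 and Appendix A2 were written to avoid that test, because it depends on the arm.

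A control with confirmed, SBRT-suitable progression between visits could therefore lose scheduled tumour assessment with no PFS event on record. What follows is left open. The progression might be recorded as the event, the patient might be censored when imaging stops, or the true event might be found late. Each of these affects the control arm only. The same hazard ratio feeds the futility rule in Section 13.4.

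**Working it through.** **1. The passages side by side.** Take one finding in each arm: between visits, a scan confirms progression of up to 5 extra-cranial lesions. All are 7 cm or smaller and SBRT-suitable, and no palliative intervention is needed.

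- *Section 4.1 and Appendix A2:* no PFS event in either arm.
- *Section 10.3, disease-progression paragraph:* the primary endpoint is not met, so assessments continue in either arm.
- *Section 10.3, between-visit rule, SBRT arm:* if the patient remains suitable for repeat SBRT, the condition is not met and scheduled imaging continues.
- *Section 10.3, between-visit rule, control arm:* the condition is met by allocation alone, and the patient moves to Section 10.4.

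Reading progression in the between-visit rule as primary-endpoint progression does not remove the conflict. The parenthesis would then be unnecessary, yet it names the control group as an alternative to an unsuitable lesion. The opening of Section 10.3, which runs follow-up until progression is confirmed without saying which kind, has the same ambiguity.

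**2. The plan's own figures (Section 13.1).** Inputs: two-sided 5%, 90% power, 2:1 allocation, medians of 3 and 6 months (HR 0.5).

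- Schoenfeld events: (1.960 + 1.282)² / [(2/3)(1/3)(ln 0.5)²] = 10.51 / 0.1068 = 98.4, so 99 against the stated 97. Power with 97 events is 0.896.
- Exponential event probabilities under the stated accrual and a 42-month total are 0.956 (control) and 0.837 (SBRT). Expected events are 37 × 0.956 + 73 × 0.837 = 35.4 + 61.1 = 96.5.

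The stated design reproduces: "110 randomised patients (anticipated 73:37) in total is required to obtain 97 PFS events". The point does not touch it.

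**3. Illustration of size.** The protocol gives no affected share, so 10%, 20% and 30% of controls are assumed (about 4, 7 and 11 of 37). The suitable progression is placed at 30-90% of the patient's own PFS time. There were 2,000 simulated trials of 73:37 per row, with the protocol's accrual. The null sets both medians to 3 months.

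| Handling | Share | HR, design effect | Power | HR, null | Null trials favouring SBRT |
|---|---|---|---|---|---|
| None affected | 0 | 0.496 | 0.895 | 0.992 | 3.2% |
| Recorded as event | 10% | 0.477 | 0.936 | 0.955 | 3.5% |
| | 20% | 0.457 | 0.950 | 0.909 | 6.9% |
| | 30% | 0.441 | 0.976 | 0.874 | 9.7% |
| Censored | 10% | 0.533 | 0.809 | 1.065 | 1.1% |
| | 20% | 0.572 | 0.666 | 1.148 | 0.3% |
| | 30% | 0.627 | 0.480 | 1.249 | 0.2% |
| Found 1-3 months late | 10% | 0.518 | 0.877 | 1.041 | 1.5% |
| | 20% | 0.537 | 0.809 | 1.103 | 0.7% |
| | 30% | 0.563 | 0.762 | 1.154 | 0.5% |

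The nominal one-sided rate is 2.5%. The simulation error near 3% is √(0.032 × 0.968 / 2000) ≈ 0.4 points, so 3.5% cannot be told apart from the 3.2% base run.

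**4. Dependence on the model.** The timing assumption matters in both directions.

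- *Censored, but unrelated to prognosis:* the HR stays at 0.5 and only control events are lost. With SE = √(1/[35.4(1 − f)] + 1/61.1), power is 0.91 at f = 0, 0.89 at 10%, 0.86 at 20% and 0.83 at 30%. This loss is much smaller than in the table.
- *Recorded as events, arising as an independent competing hazard:* the null HR is 1 − f. With 37 × 0.956 = 35.4 and 73 × 0.956 = 69.8 events, SE = √(1/35.4 + 1/69.8) = 0.206. The false-positive rate is Φ(−1.96 − ln(1 − f)/0.206): about 4% at f = 5%, 7% at 10% and 19% at 20%. This is larger than in the table.

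**The case against.** The strongest reply is that Section 10.3 does not define the event. Section 4.1 and Appendix A2 do, for both arms, and nothing in Section 10.3 tells a site to record one. This stands. Recording a suitable control progression as a PFS event would breach Section 4.1, so that branch describes an error the wording invites, not one it orders. Central review is only a partial safeguard. Section 4.1 says the virtual MDT should review progression events, but Section 3 makes this optional at local request and Section 6 limits it to where necessary. Nor can it review scans that were not taken.

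The rule is also narrow. It concerns progression suspected more than 1 month before a visit, typically on symptoms, and symptomatic progression that needs palliative intervention is already an event in either arm. This stands and limits the number affected. It does not reduce it to nothing, because every control enters with 1 to 5 progressing, SBRT-suitable lesions that trial SBRT does not treat.

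Finally, routine scans may continue. Section 4.1 asks for radiological assessment at each clinic visit, and Section 10.4 still captures deaths and treatment changes. This makes late detection a plausible outcome beside counting and censoring. It softens the problem without removing it, since neither Section 10.4 nor the schedule requires imaging.

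A reader might infer that the trial is biased towards SBRT with a grossly inflated error rate. The competing-hazard formula above does give about 50% at f = 33% and 92% at f = 50%. The documents do not support that inference. It applies the problem to a third or a half of all controls, assumes every such case is recorded contrary to Section 4.1, and rests on one timing model. A reader might also infer that Section 4.1 says outright that SBRT-suitable progression is not an event. It does not. That follows from its event list with Appendix A2 and Section 11.6, and it fails for symptomatic cases needing palliative intervention.

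**Conclusion.** The contradiction is real and lies in the stated text. Followed literally, the between-visit rule makes ascertainment of the primary endpoint depend on the arm for controls whose between-visit progression is SBRT-suitable and is not otherwise an event.

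The size is unknown. The direction is undetermined: towards SBRT if these progressions are recorded as events, and against SBRT with loss of power if they are censored or the true event is found late. The simulated ranges rest on assumed shares of 10-30% of controls and on one timing model. Step 4 shows that another model moves them either way, and effects are smaller at lower shares. They show that a handful of patients among about 35 expected control events can matter. They do not estimate what happened in this trial. The sample size is unaffected.

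**What to change.** Reconcile the passages on endpoint assessment as follows:

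- Make the between-visit rule in Section 10.3 turn, in either group, on progression meeting the primary endpoint under Section 4.1 and Appendix A2, in place of the parenthesis that names the control group.
- Align the opening of Section 10.3 so that the progression that ends scheduled follow-up is the same one.
- State that patients in either group without such an event remain on the scheduled tumour assessments.
- For controls already moved to Section 10.4, retrieve existing routine scans so that the event can be classified and dated under Section 4.1 and Appendix A2.

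The cost is a short amendment, a site memo and some retrospective scan upload. Three-monthly follow-up is already aligned with routine care, and the change concerns assessment only, not treatment.

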10.4 Procedure upon further Disease Progression

All patients will continue background TKI treatment until a change in systemic therapy is indicated. This will be according to local clinical assessment and as per standard of care. Information regarding the local criteria used to determine a change in systemic treatment will be requested with details being provided by sites using the appropriate HALT eCRF.

Patient status will be reviewed at routine clinical visits until death. The following information should be recorded on the appropriate eCRF at each scheduled visit.

- Patient status
- Current treatment
- Assessment of toxicities required at first 3 month visit post disease progression and at 1 year after last dose of radiotherapy treatment (for SBRT arm only).

Upon confirmation of disease progression the following should be collected:

• Blood samples for ctDNA analysis

10.5 Discontinuation from Treatment

Participants may discontinue from trial treatment at any time at their own request, or they may be discontinued at the discretion of the Principal Investigator. Reasons for discontinuation may include:

- Disease progression or recurrence
- Unacceptable toxicity
- Pregnancy

Participants who discontinue treatment should continue to be followed up as detailed above.

10.6 Discontinuation from Follow-up

If a patient withdraws from further follow-up the appropriate eCRF form should be submitted to ICR-CTSU stating whether the patient simply no longer wishes to attend trial follow up visits (but retains

consent for future data collection from medical records) or whether the patient has withdrawn consent for further information to be sent to the ICR-CTSU. In the very rare event that a patient requests no further follow-up data collection, the implications of this should be discussed with the patient first to ensure that this is their intent and, if confirmed, ICR-CTSU should be notified in writing.

HALT Protocol

ICR-CTSU

10.7 Schedule of Assessments

	Pre-tria	al entry				3 mo	nthly follo visits ^e	ow-up			
Visit/Assessment	Pre-registration	Screening ^a	Baseline ^b	Post-fraction 1 of SBRT ^c	8 weeks follow-up ^d	5 month follow up (First 3 monthly follow-up)	8 month follow up (Second 3 monthly follow-	Further 3 monthly follow-ups	Pre-repeat SBRT °	Disease progression	Post-progression follow-ups
Informed Consent	X										
CT Chest / Abdomen / Pelvis or PET-CT confirming OPD ^f	Х										
Contrast enhanced CT /MRI Brain		X									
Karnofsky index/ECOG PS		x	Xi		Х	Х	Х	Х	Х		
Medical History		Х									
Physical examination (height, weight, blood pressure)		X	Xi								
Full blood count, urea, electrolytes and Liver function tests		x	Xi		Х	X ⁿ					
Pregnancy test		Х									
Liver OPD lesions only: INR and DMSA ^g		Х	Xi						Х		
Lung OPD lesions only: Pulmonary function tests (FEV1, FVC and TLCO), baseline O ₂ stats, baseline dyspnoea score		х	Xi						х		
Adrenal OPD lesions only: DMSA ^g , baseline cortisol		Х	Xi						Х		
Baseline conditions			Х								
Tumour imaging	X ^h				X	XI	XI	Χ '			
Tumour assessment					Х	Х	Х	Х			
Toxicity assessment			Х		Х	Х	Х	Х			X °
Quality of Life questionnaire			X ^j		Х	X ⁿ					
Research blood samples			Х	Х	X ^m	Х	Х			X ^m	
Tissue samples			X ^k							X ^k	
Patient health status										Х	Х
Current treatment										Х	Х

ICR-CTSU

Footnotes

- ^a All assessments to be conducted within 30 days prior to randomisation unless otherwise indicated
- ^b To be completed after eligibility has been confirmed
- ^c SBRT patients only
- ^d The first visit will occur 8 weeks (+/- 5 days) after date of randomisation
- ^e Subsequent visits will occur 3 monthly there after (+/- 5 days)
- ^f Imaging assessments should be conducted ideally within 14 days, but at least within 1 month prior to registration
- g A DMSA is recommended to assess differential kidney function where exposure of one of the kidneys to high doses is expected. Appropriate alternative methods of assessment are permitted according to local clinical guidelines. Only required at pre-randomisation timepoint

^h – Additional imaging according to lesion location (e.g. MRI spine - optional) required if previous scan is > 1 month prior to registration

- ⁱ Tests are not mandated at this time point but consideration should be given as to their necessity prior to each course of SBRT treatment (initial, subsequent on further oligoprogression).
- For further details please refer to the HALT RT Planning and Delivery guidelines. Any assessments should be conducted <7 days prior to treatment
- ^j The baseline quality of life questionnaire should be completed after randomisation, prior to patient awareness of treatment allocation
- ^k Archival block or biopsy samples to be collected if patient has consented to donate tissue samples
- Anatomical sites imaged at point of enrolment should continue to be assessed at follow-up assessments (i.e. brain metastases)
- ^m Research blood samples will be collected from patients receiving SBRT after delivery of the first fraction. For all patients a sample should be collected upon progression
- ⁿ First 3 monthly visit only, not required thereafter

 Toxicity assessment required at first visit post disease progression and at 1 year after last dose of radiotherapy treatment (for SBRT arm only)

11 TRIAL TREATMENT

Patients will be randomly allocated 2:1 to receive SBRT plus continuation of background TKI (SBRT treatment group) or continuation of background TKI alone (control group).

11.1 Continuation or interruption of background TKI during SBRT course

Current uncertainty exists regarding the safety of concomitant use of TKI during SBRT treatment. Whilst a break in background TKI therapy whilst receiving SBRT treatment is aimed at minimising the risk of radiation toxicity associated with simultaneous administration of SBRT and TKI, the risk of disease flare whilst off TKI is also a considerable concern. A survey of UK and European oncologists conducted as part of the development of HALT indicated no consensus of opinion as to the best approach. Centres participating in HALT will therefore be given the option to either continue background TKI treatment alongside SBRT or stop TKI treatment during SBRT (with a minimum break of one day before the first SBRT fraction and one day after delivery of the last fraction).

Prior to commencing recruitment for the trial all centres must indicate their chosen policy as to whether they opt for a break in TKI therapy for all patients randomised to receive SBRT or whether they opt to continue administration of TKI during SBRT for all patients randomised to receive SBRT. For centres opting to interrupt TKI therapy during SBRT treatment patients must stop TKI at least one day prior to the first dose of SBRT and re-commence no earlier than one day after the last dose of SBRT. For centres opting to continue TKI therapy during SBRT treatment no changes to dose or frequency of TKI therapy is required.

11.2 Treatment timelines

SBRT treatment should commence within 4 weeks post randomisation. Appointments for fiducial marker insertion should be booked in advance of randomisation to avoid delays in commencing SBRT treatment.

11.3 SBRT Planning

Radiotherapy planning should be carried out in accordance with the guidelines in the current version of the HALT Radiotherapy Planning and Delivery Guidelines document, available on request from ICR-CTSU ([contact]).

11.4 Treatment technique

Highly conformal treatment planning is a pre-requisite for SBRT. SBRT may be delivered using a specialist SBRT platform, such as CyberKnife or with a linear accelerator with SBRT capabilities. Any SBRT delivery platform is acceptable as long as the individual centre has demonstrated they are able to comply with the radiotherapy standards laid out in this protocol and the HALT Radiotherapy Planning and Delivery Guidelines document.

11.5 Dose prescription

The recommended dose and fractionation options that can be used are detailed within the current version of the HALT radiotherapy and quality assurance guidelines. Where a range of doses is provided it is advised that the maximum dose that can be achieved whilst meeting the OAR planning constraints is prescribed.

11.6 SBRT Scheduling

Initial SBRT treatment should commence within 4 weeks of randomisation, subsequent rounds of treatment (as necessary upon further progression not meeting the primary endpoint) should be scheduled as per local guidelines. SBRT can start on any day of the week and will be delivered as per the table above and detailed in the HALT Radiotherapy Planning and Delivery Guidelines document, where the maximum number of days treatment should be delivered being dependent on the dose fractionation schedule being used. If the maximum duration for the SBRT course is exceeded due to patient or radiotherapy service delivery factors please contact the HALT trial manager ([contact]).

